Principal investigator: [name]

Protocol Title: Assessing Cognitive Improvements, Brain Neuroplasticity and the Role of Genetic Factors After Aerobic Exercise in Sedentary Adults

IRB Number: 20180926

NCT: NCT03804528

Document Version Date: 2/22/2021

IRB Study Number: 20180926

1) Protocol Title

Assessing Cognitive Improvements, Brain Neuroplasticity and the Role of Genetic Factors After Aerobic Exercise in Sedentary Adults

2) Objectives

The overall goal of the proposed study is to evaluate the effects of an 8-week aerobic exercise program on cognition and determine the relationship between cognitive improvements and neuroplasticity. Limited to Option A (See Study Options section), we will also explore the effect modification of BDNF levels and BDNF allelic status, and APOE4 status on cognitive response after exercise.

Aim 1: Quantify improvements in cognitive performance after 8 weeks (150 min per week) of moderate intensity aerobic exercise in sedentary adults ≥ 55 years of age. **H1:** We hypothesize that we will see improvements in overall cognitive performance after exercise, and greater improvements in some of the cognitive domains (e.g., in executive function and processing speed, as opposed to memory or language).

Aim 2: Determine an association between changes in plasticity, aerobic capacity, and cognitive performance overall and by cognitive domain, after 8 weeks of moderate intensity aerobic exercise in sedentary adults ≥ 55 years of age. **H2:** We hypothesize that a greater response in the brain plasticity will be associated with greater improvements in cognitive performance overall and in executive function after exercise.

Aim 3 (Option A): Explore the effect modification of BDNF (levels and Val66Met) and APOE e4 on cognitive response after exercise. **H3:** We hypothesize that individuals with greater levels of BDNF, being Val carriers or APOE e4 carriers will have greater improvement in cognitive performance after exercise.

3) Study Plan/Options

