 - The TMS-EEG integration provides real-time information on cortical reactivity and connectivity. EEG provides exquisite temporal resolution, a direct measure of neuronal activity, and is capable of differentiating inhibitory and facilitatory effects in response to TMS. Contrasting the results of TMS on EEG before and after TBS provides information about cortical plasticity (at the site of stimulation) and resulting network dynamic adaptations.
 - Brain functional connectivity and inter-regional coordination can be directly estimated from EEG's. Spontaneously occurring potentials across EEG channels will be detected prior and following stimulation using already developed event detection algorithms. Measurements following single-pulse TMS provide insights on cortical excitability. The EEG cap will be placed at the beginning of the session and will remain on for the duration of the visit.
- **tACS/EEG Plasticity**
 - An index of change in the tACS-induced modulation of cortical excitability will be defined for each participant. Brain functional connectivity and inter-regional coordination can be directly estimated from EEG's. Spontaneously occurring potentials across EEG channels will be detected prior to and following stimulation using already developed event detection algorithms.

Cognitive performance

- Cognitive performance will be assessed using a neuropsychological test battery. Executive function will be assessed using the Digit Span subtest of the Wechsler Adult Intelligence Scale – Fourth³⁰, processing speed will be assessed using the Trail-Making Test Part B³¹ and the Stroop color-word test²⁹, global cognition will be assessed with the repeatable neuropsychological battery (RBANS)³⁰; and the Delis-Kaplan Executive Function System (DKEFS)³¹ will test for language.

IRB Study Number: 20180926

- Option B: the same cognitive battery, except for the Stroop color-word test, and with the addition of a TestMyBrain.org³² battery of Digit Symbol Matching, Simple and Choice Reaction Time, and Gradual Onset Continuous Performance Test will be used via a secured Zoom Platform.

Gait and postural control

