With a significance level of 0.05, our sample of 80 individuals will provide 80% power to detect a Cohen effect size of 0.36 using a two-sided paired t-test for **Aim 1**, the effect size associated with improvements in executive function in a recent meta-analysis of healthy adults 55+,⁴² and an attrition of 20%, not uncommon in exercise intervention trials. In addition, a sample of 80 participants will provide 80% power to detect a correlation of 0.34 between the change in TMS neuroplasticity and the change in cognitive performance for **Aim 2**, and 80% power to detect an R-Squared of 0.11 attributed to a genetic modification in the change in cognitive performance using an F-Test for **Aim 3 (Option A only)**. We expect an overall improvement in cognitive performance after aerobic exercise. Most robust improvements are expected in executive function as previously shown in elderly, but also in other cognitive domains such as processing speed and attention.¹¹

Baseline characteristics will be summarized as means \pm standard deviation or medians (interquartile ranges) for continuous variables and as frequency (%) for categorical variables. Normality for the distributions of continuous variables will be visually assessed and statistically tested. If the normality assumption is questionable, Box-Cox transformation will be used to reduce the skewness in the indicated analyses or non-parametric tests will be used. All statistical tests will be conducted against a 2-sided alternative hypothesis, employing a significance level of 0.05.

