In the univariate analysis, we will compare the cognitive performance (overall and by domain) before and after exercise, using paired t-test to test for **Specific Aim 1**. For **Specific Aim 2**, we will examine the relationship between the change in TMS neuroplasticity and the change in cognitive performance using Pearson product-moment correlation coefficient. For **Specific Aim 3**, we will compare mean change in cognitive performance across subgroups by genotype using F- test. In the multivariable analyses, we will adjust for baseline characteristics (age, sex, race- ethnicity, education) using mixed effect modeling to quantify improvements in cognitive performance after exercise (**Specific Aim 1**), and to determine an association between changes in TMS plasticity, cognitive performance and changes in aerobic capacity (**Specific Aim 2**). We will use modification models by including interaction terms (time-by-genotype) to explore the relationship between change in cognitive performance after exercise and BDNF levels, Val66Met, and APOE e4 status (**Specific Aim 3-Option A only**).

12) Provisions to Monitor the Data to Ensure the Safety of Subjects*

Monitoring the safety of participants with respect to TMS neuroplasticity assessment

TMS has been used in a growing number of laboratories worldwide since 1984. A series of adverse events have been identified since then, and have been thoroughly reviewed for the development of recommended safety guidelines and precautions for the use of TMS, first at a consensus conference at the NIH in June, 1996 and, more recently, in 2008 in Siena (Italy), in a

IRB Study Number: 20180926

meeting of an international panel of TMS experts ([The Safety of TMS Consensus Group](#)).

The principal investigator will ensure that these guidelines are well-known by all study investigators and will carefully follow these updated safety guidelines in the present study. Additionally, we will track and report any adverse events that may occur.

Monitoring the safety of participants with respect to tACS neuroplasticity assessment

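### H1 predicts that some cognitive domains improve more than others, but the analysis plan specifies no comparison between domains.

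*Combined protocol and SAP*

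**What the plan says.** Section 2 (Objectives, Aim 1) gives H1 two parts: overall cognition improves, and there are "greater improvements in some of the cognitive domains (e.g., in executive function and processing speed, as opposed to memory or language"). The Data Analysis part of section 11 returns to the second part: "Most robust improvements are expected in executive function as previously shown in elderly", with processing speed and attention also expected to gain.

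For Aim 1 the same section specifies two analyses:
- Univariate: "we will compare the cognitive performance (overall and by domain) before and after exercise, using paired t-test".
- Multivariable: adjustment for age, sex, race-ethnicity and education, "using mixed effect modeling to quantify improvements in cognitive performance after exercise". The covariates are listed; the time and domain terms are not.

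The only interaction named belongs to Aim 3: "We will use modification models by including interaction terms (time-by-genotype").

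Section 8 (Cognitive performance) assigns tests to domains: "Executive function will be assessed using the Digit Span subtest of the Wechsler Adult Intelligence Scale", and "processing speed will be assessed using the Trail-Making Test Part B" together with Stroop. RBANS is global cognition and D-KEFS is language. For remote participants the section says "Option B: the same cognitive battery, except for the Stroop color-word test", with TestMyBrain tasks added.

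**The concern.** The second part of H1 is a statement about a difference between changes. Every analysis specified for Aim 1 concerns change within a score. Followed as written, the plan leaves a reader to see which domains cross 0.05 and which do not, and it gives no rule for turning that pattern into a conclusion. One domain significant and another not is weak evidence that they differ, because each test has its own chance of missing a real effect.

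Two errors are possible. Selective improvement may be claimed when all domains improved alike, or a real difference may be missed because the p-value pattern came out untidy.

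A comparison also needs settled domains, and sections 8 and 9 do not agree on which test measures what.

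**Working it through.** **Inputs.** From the plan: 80 participants, 20% attrition, two-sided 0.05, effect size 0.36 for a paired t-test. Assumed, because the documents give no values: other effects (0, 0.18, 0.25), and a common correlation r of 0, 0.25 or 0.5 between domain change scores. Effects are mean change divided by SD of change (dz).

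**The plan's own figure.** Completers: n = 80 × 0.8 = 64. Noncentrality: 0.36 × √64 = 2.88 on 63 degrees of freedom. Power is 0.809, so the stated 80% reproduces. It applies to change within one score.

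**Equal improvement in all four domains.** Let p be the chance that one domain shows significant improvement: 0.504 at dz 0.25 and 0.809 at dz 0.36. At r = 0 the patterns follow directly:
- One chosen favoured domain significant and one chosen comparator not: p(1−p) = 0.250 and 0.154.
- More favoured than other domains significant: with b₀ = (1−p)², b₁ = 2p(1−p) and b₂ = p², the chance is (1 − b₀² − b₁² − b₂²)/2 = 0.312 and 0.237.
- Strict pattern (both favoured significant, neither comparator): p²(1−p)² = 0.062 and 0.024.

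Simulation extends this to r = 0 / 0.25 / 0.5:

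| Reading | dz 0.25 | dz 0.36 |
|---|---|---|
| One chosen pair | 0.253 / 0.208 / 0.169 | 0.151 / 0.136 / 0.111 |
| More favoured than other | 0.313 / 0.281 / 0.237 | 0.236 / 0.202 / 0.163 |
| Strict pattern | 0.063 / 0.046 / 0.033 | 0.024 / 0.024 / 0.020 |
| Direct contrast, two-sided | 0.046 / 0.050 / 0.047 | 0.049 / 0.049 / 0.046 |

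About half of the last row, 2.5%, falls in H1's direction. The contrast uses a jackknife standard error. A plain t-test on scores divided by their sample SDs rejects in 5.6-6.6%.

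**True differences.** With unit change SDs, the mean of two domains minus the mean of two others has variance (1−r)(1/2 + 1/2) = 1−r. The contrast effect is therefore the difference in means divided by √(1−r). For 0.36 against 0 this gives known-SD power of 0.81 / 0.91 / 0.98. Estimating the SDs lowers it slightly:

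| Favoured pair vs comparators | Contrast power | Strict pattern |
|---|---|---|
| 0.36, 0.36 vs 0, 0 | 0.789 / 0.893 / 0.973 | 0.618 / 0.631 / 0.656 |
| 0.36, 0.18 vs 0, 0 | 0.549 / 0.673 / 0.836 | 0.230 / 0.238 / 0.245 |
| 0.36, 0.36 vs 0.18, 0.18 | 0.275 / 0.345 / 0.482 | 0.324 / 0.315 / 0.308 |

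If one comparator, such as verbal fluency, improves by 0.36 and the other not at all, the mean difference is 0.36 − 0.18 = 0.18. This is the same as in the third row, and power is about 27-48%.

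**Scale.** Change SD in baseline-SD units is √(2(1−pre-post correlation)): 0.548 at an assumed 0.85 and 0.775 at 0.70. Equal dz of 0.25 is then 0.137 against 0.194 baseline SD. A baseline-scaled contrast is significant in 10-25% of such trials (dz 0.25 to 0.36). That is not a false-positive rate. The two scales ask different questions.

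**Test labels, section 8 against section 9.**
- Digit Span: executive function in section 8; attention and working memory in section 9.
- Trails: part B is processing speed in section 8; section 9 adds task switching.
- Stroop: processing speed in section 8; response inhibition in section 9; absent in Option B.
- Language: D-KEFS in section 8, but section 9 uses it for verbal fluency including category switching, and RBANS has its own Language index.
- Memory: no test assigned in section 8; measured only through RBANS Immediate and Delayed Memory.

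**The case against.** Aim 1 is to quantify improvement, and H1 introduces its domains as examples. The study is single-arm and open-label, and is meant to supply data for a later grant application, so per-domain estimates may be all that is needed. This has force: labelling the clause descriptive is a legitimate remedy. But calling the domains examples does not remove the assertion that some improve more than others.

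A reader might infer that the mixed model excludes a domain-by-time term. The text does not support that. It gives no model terms for Aim 1 at all, so the accurate statement is that none is specified. A reader might also take the Data Analysis section to repeat the full executive-and-speed versus memory-and-language contrast. It names neither memory nor language.

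The contrast is also not uniformly better at showing H1's pattern. When the comparators change by half as much and r = 0, the strict pattern appears slightly more often (0.324) than the contrast is significant (0.275). That stands, although the pattern is still not a test of a difference.

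Finally, with no control group a domain difference may reflect retest gain. If retest adds 0.1 or 0.2 more in the favoured domains, the contrast is significant in 12-19% or 34-59% of trials. Separate tests share this weakness, and the contrast does not cure it.

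**Conclusion.** The omission is real and should be fixed. The specified by-domain tests cannot answer the comparative half of H1. Under equal improvement, a lenient reading of separate p-values favours H1 in about 16-31% of trials (more favoured than other domains significant), against about 2.5% for a direct contrast. Those figures rest on 64 completers, assumed dz of 0.25 to 0.36, assumed change correlations of 0 to 0.5, and equal retest gain across domains.

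It would go too far to say that Aim 1 as a whole lacks a valid analysis. The overall-improvement half has its paired t-test, whose stated power reproduces.

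**What to change.** 1. **Fix one test-to-domain map before analysis**, reconciling sections 8 and 9 and using tests common to Options A and B. Settle Digit Span, Trails, D-KEFS fluency against the RBANS Language index, and memory through RBANS Immediate and Delayed Memory. Settle Stroop's label too; its absence from Option B keeps it out of a shared contrast.
2. **Add one contrast to the Data Analysis section**, or the equivalent domain-by-time term: mean standardised change in executive function and processing speed minus that in memory and language, two-sided 0.05, with a 95% confidence interval. State in advance whether change is scaled by SD of change or by baseline SD, and report the other as a sensitivity analysis. Use a standard error that allows for estimated SDs; the jackknife is one option.
3. **Base any claim that domains differ on that contrast**, not on separate p-values. If the investigators do not want it, label H1's domain clause descriptive, report per-domain changes with confidence intervals, and make no claim of differential improvement.

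This needs no extra visits or participants. The plan should state the costs: a two-versus-two contrast commits the study to one reading of H1; power falls to about 27-48% if the comparators improve by half as much or fluency behaves like executive function, so a non-significant result would be weak evidence of equality; and differential retest gain remains.

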This is an investigator-initiated open label study in neurologically healthy sedentary adults. Participants will undergo a total of 29 or 31 sessions, including the screening session, three to four pretest (baseline) assessments, 24 aerobic exercise sessions and three to four post-test assessments. For option A, assessments will take place at the Neuromotor Plasticity Lab located at Lois Pope Life Center located at [name] and aerobic exercise visit will take place at either the UMMSM Medical Wellness Center or the UM Coral Gables Wellness Center. For option B, assessments and exercise sessions will take place in the participant home as they are monitored by a trained study member. An illustration of the experimental design is provided below:

Methods:

Subjects will participate in the Option A pending appropriateness based on current University of Miami recommendations and standard operating procedures as it relates to the COVID-19 pandemic. Given the COVID-19 pandemic, it is worth of note that potential participants may remain less enthusiastic about in-person procedures for an undetermined length of time. Thus, even in the event that the study team obtains approval to resume activities as per Option A based on University guidelines, we would like to continue to offer Option B according to participant preference. All testing procedures described for the Option A will be adapted (as feasible) for the Option B. Testing procedures that differ for the Option B are described and noted in the Option B methods.

OPTION A METHODS

TMS Plasticity

Subjects will come in for a total of 2 plasticity visits (pre and post training). We will measure plasticity in the motor cortex of the dominant hand.

Subjects will be set up in a chair with EMG electrodes placed on the first dorsal interosseus (FDI) on the dominant hand to measure motor threshold over in the corresponding (contralateral) motor cortex (M1). The motor threshold serves as the basis for the following TMS-measures over the motor cortex. When administering TMS, the figure of eight coil will be placed tangentially to the scalp with the handle pointing posterior for all stimulations. We will proceed with determining motor threshold and conduct TMS (single pulse TMS and TBS) over the dominant motor cortex. After removing the EMG equipment from the subject, a post TMS safety evaluation will be conducted.

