Subjects will be set up in a chair with EMG electrodes placed on the right hand for collection of motor evoked potentials (MEPs) during stimulation over the left primary motor cortex (M1). The EMG electrodes will remain in place throughout the TMS session. In order to keep the brain target constant throughout the stimulation session, we will use a frameless stereotactic neuronavigation system.

Baseline EEG Measures:

A 64 channel, TMS compatible EEG system will be set up at the beginning of the visit. Resting state EEG measures will be collected that includes a 3.5-min recording with eyes opened followed by a 3.5-min recording with eyes closed.

TMS with EEG measures:

Assessment of Motor Threshold:

Resting motor threshold (RMT) will be determined by applying single pulses of TMS to M1. RMT will be defined as the minimum stimulus intensity that produces a motor evoked potential (MEP) of at least 50 μ V and up to 1 mv in the hand muscles in at least 5 of 10 trials. MEPs will be measured by electromyography (EMG) during relaxation of the tested muscles. Determination of RMT will be used to guide intensity to be used for single and paired pulses as described below. The optimal position for obtaining MEPs will be identified at the beginning of the assessment of RMT.

TMS Assessments of Intracortical Inhibition and Facilitation Using Single TMS Pulses:

Cortical reactivity will be assessed by applying paired and single pulses of TMS to the cortex and intracortical inhibition and facilitation will be assessed using a paired pulse technique. Paired pulse techniques measure the influence of a sub- or supra-threshold conditioning TMS pulse to M1 or DLPFC on a supra-threshold TMS pulse to M1 or DLPFC. TMS intensity will be set at 120% of each individual's resting motor threshold for reactivity measures with single pulses and sub- and supra-threshold TMS pulses will be set to 80% and 120%, respectively for paired pulse measures. Cortical reactivity will be assessed via EEG measures (TMS-evoked potentials - TEPs) and cortico-motor reactivity will be assessed at M1 by measuring peak-to-peak amplitude of MEPs (motor-evoked potentials as measured by EMG) induced in the hand muscles in response to the TMS.

Neuropsychological Test Battery

Participants will undergo 2 neuropsychological test visits (pre-test and post-test) to assess the influence of physical exercise on cognitive performance. This assessment will last approximately 1.5

hour.

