- Global Cognition: The **Repeatable Battery for the Assessment Neuropsychological Status (RBANS) Update**³⁰ is a brief battery used to measure an individual's cognitive state. The battery is composed of five cognitive domains including: Immediate memory, Visuospatial/Constructional, Language, Attention, and Delayed Memory. The whole assessment is completed in approximately 25 minutes.
 - Immediate memory is assessed through a list learning task of 10 words and a short story. Participants are asked to repeat a list of 10 words over a series of four learning trials. The score is dependent on the number of correctly recalled words over the four trials. Participants are then read a short story and asked to recall as many details from the story that they can remember over 2 trials. The score is based on the number of correct key details the participant can recall.
 - Visuospatial/Constructional is assessed using a figure copy and line orientation task. Participants are asked to copy a figure as accurately as they can while being timed. The score is based solely on the exactness of the copy of the figure. Participants are then shown 13 lines that are numbered 1 to 13 and are arranged in a fan shape that are 15 degrees apart from each other at the top of a page. Participants are shown a series of two lines, isolated from the fan shape, and asked to identify what numbers they correspond to on the fan shape. Participants are awarded one point for each time they correctly match the lines.
 - Language is assessed through picture naming and semantic fluency. Participants are asked to identify the name of ten different figures. The score is based on the number of figures the participant names correctly. Participants are then asked to name as many items from a specific category as they can for one minute. One point is awarded for each unique response.

IRB Study Number: 20180926

- Attention is composed of a digit span and coding task. Participants are read a series of numbers increasing in length in which they are asked to repeat. Participants are awarded one point for each series of number they correctly recall. Coding is comprised of a key of nine symbols that are associated with a number one through nine. The participant is then asked to use the key to assign numbers to a list of matching symbols below, where the numbers are missing. One point is given for each symbol correctly assigned to a number based on the key.

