A test of maximal aerobic capacity will be obtained using the Incremental Shuttle Walking Test³⁸ and prediction equations to determine VO² peak changes over time. [name], PT, PhD Professor of Physical Therapy and a leader in cardiorespiratory fitness testing and training, will serve as a consultant on this proposal and will oversee the development and implementation of the exercise testing and training, and guide the analysis and interpretation of the results.

Blood Collection

IRB Study Number: 20180926

Blood samples will be collected for BDNF levels and DNA to assess brain-derived neurotrophic factor (BDNF) Val66Met polymorphism and the presence of apolipoprotein-E (APOE) e4 allele. We will store blood samples for future examination of other potential genetic, epigenetic, metabolic or pro-inflammatory markers. DNA will be extracted by standard methodology and the preIT L2P reagent.³⁹ The SNPs of the BDNF gene (rs6265, rs429358 and rs7412) and APOE4 will be analyzed using TaqMan genotyping assays. Blood samples will be delivered to the lab on ice within 2 hours of collection, centrifuged and stored at -80 °C until processing.

Physical exercise Intervention

The physical exercise intervention will be administered at the University of Miami Miller School of Medicine Wellness Center. Participants will be given a time slot, which will be preferred for the duration of the study but flexibility with the intervention time frame will be provided. Participants will be supervised by a member of the study team during all times and all sessions. Each participant will engage in 60 minute daily sessions delivered 3 times/week for 8 consecutive weeks (a total of 24 sessions).

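### With no comparison group, the Aim 1 analysis estimates change from before to after the programme, not the effect of exercise that the overall goal claims

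*Combined protocol and SAP*

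**What the plan says.** Section 2 (Objectives) gives the overall goal as to "evaluate the effects of an 8-week aerobic exercise program on cognition". Aim 1, in the same section, is worded more modestly: it sets out to quantify improvement after eight weeks of exercise and names no comparator.

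Section 9 (Study Design) describes an open-label study: "Participants will undergo a total of 29 or 31 sessions, including the screening session, three to four pretest (baseline) assessments, 24 aerobic exercise sessions". Under Physical exercise Intervention it adds: "Each participant will engage in 60 minute daily sessions delivered 3 times/week for 8 consecutive weeks (a total of 24 sessions". Options A and B are modes of delivery, in person or remote. Neither is a no-exercise condition.

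Section 9 (Neuropsychological Test Battery) says: "Participants will undergo 2 neuropsychological test visits (pre-test and post-test) to assess the influence of physical exercise on cognitive performance". The Postural Control assessment text gives the same purpose for posture and gait.

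Section 11 (Data Analysis) says for Aim 1: "we will compare the cognitive performance (overall and by domain) before and after exercise, using paired t-test". For the multivariable step it says: "we will adjust for baseline characteristics (age, sex, race- ethnicity, education) using mixed effect modeling to quantify improvements in cognitive performance after exercise".

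The supplied text describes no control group, waiting period, repeat baseline, retest correction or choice of test form. One instrument is named the "Repeatable Battery for the Assessment Neuropsychological Status (RBANS) Update", but that is its title and does not say which form is given when. The Option B familiarization session covers the kit, the video platform and the EEG cap and tablet, not the cognitive tests.

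**The concern.** The goal and the stated purpose of the battery are causal. They ask what exercise does to cognition. The data can answer a different question: how far mean scores moved between week 1 and week 10 in people who all exercised.

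That movement is the sum of any exercise effect and everything else that changes over the interval, including familiarity with the tests, expectation in an open-label study, regression to the mean and calendar effects. Nothing in the design or the model separates these parts. Adjusting for age, sex, race-ethnicity and education does not help, because demographic covariates cannot supply the change that would have occurred without exercise. Correlating changes within the same participants (Aim 2) does not supply it either.

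At stake is the reading of a significant Aim 1 result. Its 5% error rate protects against declaring change when there is none. It does not protect against declaring an exercise benefit when there is none.

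**Working it through.** **Inputs.** From Sections 6 and 11: 80 enrolled, 20% attrition, two-sided 0.05, paired t-test, Cohen effect size 0.36, stated power 80%. Assumed here: 0.36 is in units of the SD of the change score, and the non-exercise gains take the range of values used below. The documents give no retest figure.

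**1. The plan's own figure.**
- Completers: 80 × 0.8 = 64, so 63 degrees of freedom.
- Noncentrality: 0.36 × √64 = 0.36 × 8 = 2.88.
- Critical value: t(0.975, 63) = 1.998.
- Power: 80.9%, against 80% stated.

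The sample-size arithmetic reproduces with attrition already allowed for. It is power to detect change.

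**2. What the test declares if exercise does nothing.** Suppose the true exercise effect is zero but scores rise for other reasons by g SD of change. The probability of a significant improvement is P(T > 1.998), where T is noncentral t with 63 df and noncentrality 8g.

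| Assumed non-exercise gain g | Noncentrality 8g | Significant improvement |
|---|---|---|
| 0 | 0 | 2.5% |
| 0.05 | 0.4 | 5.9% |
| 0.10 | 0.8 | 12.1% |
| 0.20 | 1.6 | 35.0% |
| 0.30 | 2.4 | 65.7% |

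**3. What a positive result would leave open.**
- Half-width of the 95% interval for mean change, in SD of change: 1.998 / 8 = 0.25. Any observed mean change above about 0.25 SD is therefore significant.
- If the planned 0.36 is observed, the interval is 0.36 ± 0.25, or about 0.11 to 0.61.
- A non-exercise gain of 0.11 SD or more would leave that result compatible with no exercise benefit, since subtracting it brings the lower limit to zero or below.

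**The case against.** The strongest reply is that the operative text is already modest. Aim 1, its hypothesis and the analysis section all speak of improvement after exercise. The study is openly described as open label, no control is implied, and the data are partly meant to prepare for later studies and a grant submission. Single-arm studies are legitimate, no other test on these data would do better, and every gain in the table above is assumed.

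Most of this stands, and it limits the point in three ways. A reader might infer that the paired t-test is the wrong test. It is not: it is valid for Aim 1 as worded. A reader might infer that the trial's false-positive rate is inflated to the figures in the table. The documents do not support that, because they give no retest gain; the table shows how sensitive the causal reading is, not how large the bias is here. A reader might also infer that a control arm is required. The aim as written can be met without one.

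The reply does not remove the mismatch. The overall goal and the purpose of the battery are still worded as effects of exercise, and no passage limits the conclusion to uncontrolled change. The planning effect size comes from a meta-analysis that the plan associates with improvements in executive function, and the plan expects improvement. A significant result would readily be read as an exercise effect.

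**Conclusion.** The concern holds as a mismatch between claim and design. The planned analyses estimate mean change from before to after the programme. They do not support a statement about the effect or influence of exercise on cognition.

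That conclusion rests only on the design as described: all participants exercise, there is one cognitive assessment on each side, and there is no comparator. It needs no numerical assumption. The size does. With 64 completers and no exercise effect, assumed gains of 0.05 to 0.30 SD of change raise the chance of a significant improvement from 2.5% to between about 6% and 66%. At the planned effect, a gain of 0.11 SD is enough to leave no exercise benefit as a compatible explanation. Whether gains of that size occur in this battery over this interval cannot be judged from the documents.

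**What to change.** Four wording changes:

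- Section 2, overall goal: state it as describing the change in cognition from before to after an 8-week aerobic exercise programme.
- Section 9, Neuropsychological Test Battery: state the purpose as assessing change in cognitive performance from before to after the programme.
- Section 9, Postural Control assessment: make the same change for posture and gait.
- Section 11, Data Analysis, Aim 1: add that, with no comparison group, the estimated change includes any retest gain or other time effect and will not be reported as an effect of exercise.

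The cost is a less favourable claim. The paired t-test, the mixed model, the sample of 80 and the stated 80% power are unchanged, and no visits or participants are added.

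For comparison, keeping the causal goal through a 1:1 concurrent control would need 123 per arm, or 246 evaluable, at an assumed between-arm difference of 0.36 SD of change and 80% power. At 20% attrition that is 246 / 0.8 = 307.5, so 308 enrolled. With the present sample (32 + 32 evaluable), power would be about 29%. Rewording is the proportionate change.
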